6.2 Sample Size

Based on the CANONIC study, the overall 90-day mortality rate is assumed to be about 50% in the whole study population ([3](#), [6](#)). Assuming a potential drop-out rate of 10% and 5% type-1 error for a 2-sided Chi-square test, a global sample size of 380 subjects (190 per treatment group) will allow an 80% statistical power to detect an absolute reduction of 15% (a 35% 90-day mortality rate) in subjects treated with SMT+PE-A 5%.

Alternatively, the sample size was calculated based on the log-rank test as follows. Assuming the 90-day mortality rate is 50% for the control group, or equivalently, the survival rate is 50%, which translates to a hazard rate of 0.0077 assuming an exponential distribution. Using a log-rank test at the two-sided significant level of 5%, a total of 141 events would provide at least 80% power to detect an absolute reduction of 15% in mortality rate (a 35% 90-day mortality rate, or equivalently, a 65% survival rate) in subjects treated with SMT+PE-A 5%. This absolute difference in mortality rates translates to a hazard ratio of 0.6215, or an approximate 38% risk reduction. With all subjects followed for the entire 90-day duration of the study, a total of 332 subjects would be required to obtain 141 events. Assuming a dropout rate of 10%, a global sample size of 370 subjects (185 per treatment group) is required. This sample size calculation was performed using Proc Power with the "Twosamplesurvival" statement in SAS version 9.4.

Taking a conservative approach, the larger of the 2 sample sizes (i.e., the one based on the Chi-square test) will be used to ensure the study has sufficient power.

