6.5 Hypothesis Testing and Multiplicity Adjustments

All statistical tests will be two-sided with significance level fixed at 0.05.

The fixed-sequence testing method will be used to adjust for multiplicity in the analyses of the secondary efficacy endpoints (using ITT population). Specifically, the superiority of SMT+PE-A 5% versus SMT alone for the secondary efficacy endpoints will only be tested if the superiority for the primary efficacy endpoint is demonstrated at the two-sided significance level of 5% (using ITT population).

Instituto Grifols, S.A. / Protocol IG1407

For the secondary efficacy endpoints, each subsequent hypothesis is tested only if the superiority for the previous comparison(s) has been demonstrated at a two-sided significance level of 5%. The order in which the null hypotheses will be tested is predetermined for the secondary efficacy endpoints as follows:

1. Time to transplant or death through Day 90 after randomization of SMT+PE-A 5% versus SMT alone
2. Time to death through Day 28 after randomization SMT+PE-A 5% versus SMT alone

No other adjustments for multiplicity are planned. P-values will be displayed for all the above pre-specified tests for completeness; interpretation and reporting of significant hypothesis test results will follow the fixed sequence approach described.

7 Subject Disposition and Demographics

Unless otherwise noted, all demographics listings and summaries will be based on the ITT population.

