9.3.2 CLIF-C OF Score and Sub Scores for Organ Function

CLIF-C OF scores evaluated at baseline (last measurement taken prior to treatment day 1), during and after the treatment period, and at the end of hospitalization (or before liver transplantation or death) will be listed.

The CLIF-C OF score system consists of six sub-scores for liver, kidney, brain, coagulation, circulatory, and respiratory organs/systems - each with values of 1, 2 or 3 with a higher number representing more severe disease.

Each CLIF-C OF sub-score will be summarized as a categorical variable by treatment for each visit. The CLIF-C OF sub-scores will be compared at visits when the data are collected for both treatment groups using the generalized linear models implemented in SAS GENMOD procedure, in which the CLIF-C OF sub-score is modeled by the proportional odds cumulative logit model for ordinal data with adjustment for baseline sub-score, region (Europe of North America) and ACLF subgroup (ACLF-1B, ACLF-2, or ACLF-3a) treatment, visit and treatment-by-visit interaction, as independent variables), and the robust variance estimate for the treatment effect will be estimated based on the independent working correlation structure.

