9.3.8 Organ Failure at the End of Hospitalization

Organ failure is defined according to the CANONIC study criteria for each of the following organs/systems: liver, kidney, brain, coagulation, circulatory, and respiratory. Kidney failure is defined as CLIF-C OF sub-score of 2 or 3; for all others, organ failure is defined as CLIF-C OF sub-score of 3. Refer to [Appendix 4](#) for additional details. The number and percentage of subjects experiencing organ failure will be summarized for each organ by visit, and at the end of hospitalization i.e. hospital discharge visit. The percentage of subjects with each organ failure at end of hospitalization will be compared between treatment groups using the Fisher’s Exact or Chi-square test.

Assessments after Liver transplant will be removed from summaries and analysis.

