9.3.11 Exploratory Sensitivity Analyses

For ACLF course at end of hospitalization, specific organ failure at end of hospitalization, and percentage of new infections at end of hospitalization, a sensitivity analyses will be performed in which treatment effects will be adjusted for treatment group, region (Europe or North America) and 3 ACLF grades (ACLF-1b, ACLF-2, or ACLF-3a) as collected from IWRS by fitting an appropriate Logistic Regression model or by means of the Cochran-Mantel-Haenszel (CMH) test.

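### The exploratory comparison of each organ failure at hospital discharge never uses that organ's failure status at baseline, which costs power if baseline status is prognostic

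*SAP*

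**What the plan says.** SAP 9.3.8 defines failure of each organ by cutting its CLIF-C OF sub-score (2 or 3 for kidney, 3 for the others). The between-arm test is Fisher's exact or chi-square, made on the discharge assessment. The SAP sentence that names it begins: "The percentage of subjects with each organ failure at end of hospitalization will be compared between treatment groups using the". No covariate is named.

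SAP 9.3.11 adds one sensitivity analysis for this endpoint, by logistic regression or CMH, in which "treatment effects will be adjusted for treatment group, region (Europe or North America) and 3 ACLF grades" as recorded in IWRS. The organ's own baseline status is not included.

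SAP 9.3.2 collects the CLIF-C OF sub-scores at baseline. It models each ordinal sub-score by visit with a proportional-odds model "with adjustment for baseline sub-score, region" and ACLF subgroup.

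Protocol 9.1.2.4 names the same unadjusted main test. Its sensitivity analysis adjusts for baseline imbalances that are both clinically and statistically significant. SAP 9.3.11 replaces that rule with region and grade, and SAP Section 12 does not list the change.

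**The concern.** Every eligible grade (ACLF-1b, 2 or 3a) requires at least one failing organ at entry. Whether a given organ, say the kidney, is failing at discharge plausibly depends on whether it was failing at the start. An unadjusted test leaves that variation in the error term, and a chance imbalance in which organs were failing at entry passes straight into the comparison.

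ACLF grade does not fill the gap. Grades 2 and 3a count failing organs without saying which ones. The SAP adjusts the ordinal form of this measurement for its baseline value but not the binary form at discharge. At stake is the precision of an endpoint named in the exploratory objectives (Protocol 3.1.3, SAP 4.1.3).

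**Working it through.** **Inputs from the documents.**
- Significance level (SAP 6.5): "All statistical tests will be two-sided with significance level fixed at 0.05".
- Sample size (SAP 6.2): "a global sample size of 380 subjects (190 per treatment group) will allow an 80% statistical power".
- Control rate and effect for the primary endpoint (SAP 6.2): "the overall 90-day mortality rate is assumed to be about 50% in the whole study population", and power is to "detect an absolute reduction of 15% (a 35% 90-day mortality rate").
- Sizing basis (SAP 6.2): "Assuming a potential drop-out rate of 10% and 5% type-1 error for a 2-sided Chi-square test".
- Eligible-grade prevalences at diagnosis (Protocol Table 2-2): 30%, 36% and 9% for ACLF-1b, 2 and 3a, which is 40/48/12% of the 75 points.

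**Assumed, because the documents give nothing.** Organ-failure rates at baseline and discharge, the association between them, and a common odds ratio within baseline strata.

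**Step 1: the plan's own figure.** For 50% vs 35%, n per arm = [1.96·√(2·0.425·0.575) + 0.8416·√(0.5·0.5 + 0.35·0.65)]² / 0.15² = (1.370 + 0.582)² / 0.0225 = 169.3, so 170. Then 2·170/0.9 = 378, against 380 stated. The figure reproduces, but it belongs to 90-day mortality. No power is stated for organ failure.

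**Step 2: power with and without the organ's baseline status.** Let q be the share failing at baseline. Let a and b be the control risks at discharge with and without baseline failure, and a₁ and b₁ the treated risks under the common odds ratio. Then p₀ = qa + (1−q)b, p₁ = qa₁ + (1−q)b₁ and d = p₀ − p₁. Means over the arms are p̄, ā and b̄.
- Unadjusted: Φ{[d − 1.96·√(2p̄(1−p̄)/n)] / √([p₀(1−p₀) + p₁(1−p₁)]/n)}.
- Stratified on baseline status: the same form, with each p(1−p) replaced by the within-stratum variance V(x,y) = q·x(1−x) + (1−q)·y(1−y).

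Worked case: n = 190, q = 0.40, a = 0.50, b = 0.10, odds ratio 0.419.
- a₁ = 0.295, b₁ = 0.0445, p₀ = 0.260, p₁ = 0.145, d = 0.1152.
- Unadjusted: (0.1152 − 1.96·0.0412)/0.0408 = 0.84, so 80.0%.
- Adjusted: V falls to 0.1360 from p̄(1−p̄) = 0.1614 (16% removed). (0.1152 − 1.96·0.0378)/0.0372 = 1.10, so 86.5%.

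Results at 190 per arm, with the effect set in each row so that the unadjusted test has 80% power:

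| Failing at baseline | Control risk with / without baseline failure | Variance removed | Adjusted power |
|---|---|---|---|
| 40% | 20% / 20% | 0% | 80.0% |
| 40% | 30% / 20% | 1% | 80.4% |
| 40% | 40% / 10% | 10% | 84.0% |
| 40% | 50% / 10% | 16% | 86.5% |
| 40% | 60% / 10% | 23% | 89.4% |
| 40% | 70% / 10% | 32% | 92.7% |
| 10% | 30% / 5% | 5% | 82.3% |

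The trial stopped early and the SAP does not give the achieved size. With the effect rescaled in the same way, the 40%-baseline rows run from 80.0% to 92.1% at 120 per arm and from 80.0% to 91.5% at 80 per arm.

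**Step 3: does the planned grade adjustment recover this?** This was simulated with 4,000 trials per setting at 190 per arm, with control risks from 40%/10% to 70%/10% and a grade mix of 40/48/12%. The assumed chance that the organ is failing at entry was 25/45/70% by grade (0.40·25 + 0.48·45 + 0.12·70 = 40% overall). Region was not simulated.

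| Test | Power | Type I error |
|---|---|---|
| Chi-square | 79–80% | 4.6–5.0% |
| Fisher | 76–77% | 3.5–3.7% |
| CMH on ACLF grade | 80–81% | 4.9–5.1% |
| CMH on the organ's baseline failure | 84–92% | 4.9–5.4% |

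Under these assumptions grade recovers almost nothing, while the organ's own status recovers about 4 to 13 points over chi-square. If grade also affected discharge status in its own right, it would recover more than shown.

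**Step 4: cross-check by correlation.** Power = Φ[(1.96 + 0.8416)/√(1−ρ²) − 1.96] gives 80.4% at ρ = 0.1, 81.6% at 0.2, 83.6% at 0.3 and 89.9% at 0.5, in line with Step 2.

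**The case against.** The strongest reply is that the baseline information is already used. SAP 9.3.2 models all six sub-scores on the fuller ordinal scale with the baseline sub-score as covariate, and SAP 6.1.5 maps discharge assessments into the visit windows. This stands in part. A reader might infer that the trial discards its baseline organ data, and 9.3.2 shows that it does not. But 9.3.2 compares ordinal scores by study day. The end-of-hospitalization comparison is made only in 9.3.8 and 9.3.11, and neither uses the organ's baseline status.

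Second, the unadjusted test is the protocol's own method, it is valid under randomization, and the endpoint is exploratory. That stands. A reader might infer that the trial's 80% power or a confirmatory claim is at risk. The documents do not support this: the 80% relates to 90-day mortality, and organ failure lies outside the fixed testing sequence.

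Third, a reader might call baseline failure the strongest predictor, or count all six organ tests as weakened. The documents report no association of either kind. Exclusion 8v3 removes PaO2/FiO2 ≤200, which is also a respiratory-failure threshold in Protocol 7.1. Baseline respiratory failure should therefore be rare, arising through the SpO2/FiO2 criterion or the ventilation rule, and adjustment there would gain little.

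Fourth, the calculations assume that everyone randomized contributes. The endpoint is read at discharge, assessments after transplant are removed, and the SAP does not say how in-hospital deaths are counted. Protocol Table 2-2 puts 28-day mortality at 34% in these grades. This stands as a separate and possibly larger problem, which baseline adjustment does not solve.

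**Conclusion.** The point holds as an inexpensive improvement to an exploratory analysis. No planned analysis of binary organ failure at discharge uses the same organ's baseline failure, although the data are collected and the SAP already adjusts for them elsewhere.

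Starting from 80% unadjusted power, the gain is about 4 to 13 points (84% to 93%) if baseline failure is moderately to strongly prognostic. It is about 2 points in the rarer-failure example and essentially zero if baseline is weakly prognostic. All of these figures rest on assumed rates and a common odds ratio, and the adjusted test used baseline status alone, without the added grade and region terms. No confirmatory conclusion changes.

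**What to change.** In SAP 9.3.8 and 9.3.11:
- For each organ, fit a logistic model with treatment, baseline failure of the same organ (yes/no), region and ACLF grade, or use CMH stratified by that baseline failure.
- Make this the main comparison and report the odds ratio with its 95% CI.
- Keep the Fisher/chi-square test as the supportive unadjusted result.
- State a fallback for sparse organs, such as respiratory: baseline status only, or unadjusted.
- List the change from Protocol 9.1.2.4 in SAP Section 12.

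The cost is SAP wording and one added covariate, with no new data. The estimate becomes a conditional odds ratio rather than a comparison of percentages, so the percentages by arm should still be shown. The trial is open-label and its last visit (14 April 2025) precedes SAP 3.0 (15 October 2025), so the change should be dated and justified. How in-hospital deaths are counted needs its own statement in 9.3.8.

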9.3.9 New Infections at End of Hospitalization

The number of subjects with new infections by the end of hospitalization is defined as the number (and percentage) of subjects with one or more AE categorized as an infection, or any and disease related

complication i.e. spontaneous bacterial peritonitis or an infection captured as “other” and described as an infection on the disease related complications CRF page, with a start date on or after the randomization date and before the end of hospitalization i.e. hospital discharge date. The percentage is calculated for each treatment group for all subjects in the ITT population. The percentage of subjects with new infections at end of hospitalization will be compared between treatment groups using the Fisher’s Exact or Chi-square test.

9.3.10 Rate of New Infections

The annualized rate of new infections for a subject is defined as (number of infections for the subject) / (study duration in years for the subject). The study duration in days is defined as (end of study date - randomization date+1). The study duration in years also known as the person-year is defined as (study duration in days) / 365.25. A new infection is defined as an AE categorized as an infection or any disease related complication considered an infection i.e. spontaneous bacterial peritonitis or an infection captured as “other” and described as an infection on the disease related complications CRF page with a start date on or after the randomization date to the end of study. The annualized rate of new infection per subject will be summarized by treatment group as continuous variable.

The rate of new infections will be compared between treatment arms using a generalized linear model procedure for Poisson regression with adjustment for overdispersion using the Pearson statistic to estimate the scale parameter. The response variables in the model will be the number of new infections for each subject after randomization to the end of study. The model will include treatment group, region (Europe or North America) and ACLF grade (ACLF-1b, ACLF-2, or ACLF-3a) as collected from IWRS as fixed effects. The natural logarithm of the subjects’ study duration will be used as an offset variable in the model to adjust for subjects having different study durations. For each treatment group the mean yearly rate of new infections and corresponding two-sided 95% confidence intervals (CI) is presented. The estimated treatment effect (i.e. the incidence rate ratio of SMT + PE-A 5% versus SMT alone) and corresponding two-sided 95% CI will be presented also.

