- Infection surveillance using microbiology (cultures) including blood, urine, ascetic fluid, sputum, and pleural fluid. If a positive result occurs at screening, a Day 3 result will be collected. If a thoracentesis or paracentesis has been performed within the last 5 days prior to screening, results of the fluid cultures should be documented in the medical notes. Microbiology cultures will be performed at local labs and the results will be captured in the subject's source documents but will not be entered into the eCRF. All new infections will be recorded as AEs and recorded in subject's source documents and the eCRF. Additional samples will be obtained upon clinical suspicion.
- Microbiological tests (Cytomegalovirus [CMV] polymerase chain reaction [PCR], and galactomannan antigen index)
- Record ACLF grade ([Table 2-1](#))
- Illness severity scores: CLIF-C OF score, CLIF-C ACLF score, Child-Pugh score, and MELD score ([Appendix 4](#))
- Blood biomarker retains for subjects in the SMT and SMT+PE-A 5% groups
- Record prior (30 days prior to screening) and concomitant medications
- Record AEs

Subjects with ACLF-1b, ACLF-2, or ACLF-3a will be included at diagnosis of the syndrome. Subjects with ACLF-1a will be followed up and included if they deteriorate to ACLF-1b, ACLF-2, or ACLF-3a within the 10-day Screening Period. Subjects with ACLF-3b will be followed up and included if they improve to ACLF-3a, ACLF-2, or ACLF-1b within the 10-day Screening Period.

Evaluation of cardiac function at screening will be optional in subjects without vascular failure but mandatory in those with shock. This evaluation will be performed according to local guidelines.

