8.3.10 Disease Progression

In this clinical study, disease progression is defined as the worsening of a subject’s condition attributable to the disease for which the investigational product is being studied. It may be an

GRIFOLS
 
Bioscience Industrial Group
	Number	BIG-CL-PRT-000002	Version	6.0	Status	Retired	Effective Date	29-Mar-2023
	IG1407 - Effects of Plasma Exchange with Human Serum Albumin 5% (PE-A 5%) on Short-term Survival in Subjects with "Acute-On-Chronic Liver Failure" (ACLF) at High Risk of Hospital Mortality							Page
								72 of 102

increase in the severity of the targeted disease and/or increases in the symptoms of the targeted disease. Anticipated disease progression of ACLF includes, but not limited to: HE, gastrointestinal (GI) bleeding, portal hypertension, ascites, spontaneous bacterial peritonitis, HRS, and associated organ/system failure(s) (eg, liver, kidney, brain, coagulation, circulation and/or lung), which may develop at any time during the course of the disease.

The development of sequelae of ACLF and associated organ/system failure(s) during the clinical study should be considered as disease progression and not an AE, unless there is evidence suggesting a causal relationship between the study drug and the AE. Manifestations of sequelae of ACLF and associated organ/system failure(s) will be treated as disease progression and will be documented in the eCRF and subject’s medical records, but not immediately reported to the sponsor.

Hospitalization or prolonged hospitalization due to disease progression and/or the signs and symptoms of disease progression should not be reported as an SAE during the study.

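### The new-infection rate in SAP 9.3.10 pools two eCRF pages with no rule that one episode counts once, so an infection entered on both pages can be counted twice

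*SAP*

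**What the plan says.** **Counting rule.** SAP 9.3.10 defines the event by two sources: "A new infection is defined as an AE categorized as an infection or any disease related complication considered an infection". The second source is spelled out as "i.e. spontaneous bacterial peritonitis or an infection captured as" the free-text other category on the complications page. For the model, "The response variables in the model will be the number of new infections for each subject after randomization to the end of study", with the log of study duration as offset, a Pearson scale for overdispersion, and a rate ratio with 95% CI.

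**Recording rule for infections.** The infection-surveillance text in Protocol 7.2.1.1 reads "All new infections will be recorded as AEs". Protocol 7.2.1.2.3 and Appendix 1 footnote g repeat it, as do SAP 5.2.2.3 and SAP Appendix 1 footnote g. None of these places makes an exception for SBP.

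**Recording rule for SBP.** Protocol 8.3.10 lists as anticipated progression "HE, gastrointestinal (GI) bleeding, portal hypertension, ascites, spontaneous bacterial peritonitis" and further items. Sequelae of ACLF "should be considered as disease progression and not an AE, unless there is evidence suggesting a causal relationship" with the study drug, and they "will be treated as disease progression and will be documented in the eCRF". Protocol 8.3.3.1 makes the same exclusion in the AE definition. SAP 10.2 collects all disease-related complications through Day 90 and names SBP among them.

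**Companion endpoint.** SAP 9.3.9 uses the same two sources but counts subjects with at least one new infection by the end of hospitalization.

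**The concern.** The count in SAP 9.3.10 is meant to be a number of infections, but it is assembled from two pages that may hold the same infection. The protocol gives sites two answers to the question of where an SBP belongs. A site that tries to satisfy both enters it on both pages, and nothing in either document reduces the two entries to one. The count for the same clinical course then depends on local recording habit.

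The exposure is not limited to SBP. An infection written under other on the complications page is also a new infection under the surveillance text, so it too may appear on the AE page.

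The rate of all new infections is a named exploratory objective in both documents. At stake are the annualized rates by arm, the width of the confidence interval and, if recording habits differ between arms, the rate ratio.

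**Working it through.** The plan states no infection rate, SBP share or expected rate ratio, so there is no figure of its own to reproduce. The check has two parts.

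**1. One SBP under each reading of the protocol**

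| What the site follows | Entries | Count under SAP 9.3.10 |
|---|---|---|
| Disease-progression rule only (Protocol 8.3.10) | complications page | 1 |
| Surveillance rule only (Protocol 7.2.1.1) | AE page | 1 |
| Both | both pages | 2, since each entry meets the definition and no rule merges them |

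The nearest rules elsewhere do not fill the gap. Protocol 8.3.8 groups related signs and symptoms into one diagnosis when AEs are recorded, and does not link the two pages. SAP 6.1.5 resolves duplicate laboratory, vital-sign and score assessments. SAP 8.1 and 10.1 count a subject once per category. None of them merges an infection AE with a complication.

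**2. Size**

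*One subject.* By SAP 9.3.10, "The study duration in days is defined as (end of study date - randomization date+1"), divided by 365.25 for years. With the end of study 90 days after randomization, duration is 90 + 1 = 91 days.
- One episode counted once: 1 × 365.25 / 91 = 4.01 per year.
- The same episode counted twice: 2 × 365.25 / 91 = 8.03 per year.

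*Group rate.* Let s be the share of infections that could sit on both pages and q the fraction of those that do. The rate is multiplied by 1 + s·q. Neither s nor q is in the documents. Assume s = 10–30% and q from 0 to 1:
- q = 0: 1.00, no inflation.
- q = 1: 1.10 (s = 10%) to 1.30 (s = 30%).

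*Rate ratio.* It is multiplied by (1 + s·qT)/(1 + s·qC), with T for SMT+PE-A 5% and C for SMT. If qT = qC the factor is exactly 1. If they differ, it moves in the direction of the arm with more double entry. The limits of the same assumed range are 1.10–1.30 (qT = 1, qC = 0) and 1/1.30 to 1/1.10 = 0.77–0.91 (qT = 0, qC = 1). These bound an assumption and do not estimate a bias.

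*Dispersion.* Suppose episodes are Poisson and every overlapping one is duplicated. Each episode then contributes 1 with probability 1 − s or 2 with probability s. The mean contribution is 1 + s and the mean square is (1 − s) + 4s = 1 + 3s. Variance over mean is (1 + 3s)/(1 + s): 1.3/1.1 = 1.18 at s = 10%, and 1.9/1.3 = 1.46 at s = 30%, instead of 1.

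*Net effect on precision.* The variance of a log rate is dispersion divided by expected count, so it changes by (1 + 3s)/(1 + s)²: 1.3/1.21 = 1.07 and 1.9/1.69 = 1.12. Standard errors rise by about 4% to 6%, since the square roots are 1.04 and 1.06.

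**The case against.** **The protocol does not tell sites to record an SBP twice.** This stands. Protocol 8.3.3.1 and 8.3.10 say that an anticipated, unrelated SBP is not an AE, so a site following those sections makes one entry. A reader might infer from the two instructions together that every SBP is double-counted. The text does not support that: conflicting instructions make double entry possible, not required.

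**The two-source definition has a sensible purpose.** An AE-only count would miss an SBP recorded as progression, and the SAP version history shows that the infection definition was revised in version 2.0. The SAP also speaks of infections and never says that entries are summed. This is fair, but the definition makes each qualifying AE and each qualifying complication a new infection. If episodes are intended, the SAP has to say so.

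**The bias falls on one arm.** A reader might argue that an SBP suspected of being related to study drug must be entered on both pages, that this can happen only in the PE-A 5% arm of an open-label trial, and that a true ratio of 1.00 would therefore be reported as 1.10 to 1.30. The documents do not support this. The exception in Protocol 8.3.10 takes a related event out of the class of events that are not AEs; it does not ask for a second entry. The surveillance instruction applies to both arms. The 1.10 to 1.30 range also needs complete or near-complete duplication in one arm and none in the other, for which there is no evidence.

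**It matters little.** The endpoint is exploratory and outside the fixed sequence in SAP 6.5, and the Pearson scale absorbs the extra dispersion. The comparison of new infections that the protocol itself specifies, in 9.1.2.4, corresponds to the subject-level analysis in SAP 9.3.9, which a duplicate entry cannot change. All of this stands and limits the weight of the point. The Pearson scale does not, however, correct inflated rates or a biased ratio.

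**The eCRF is not in the documents.** Its completion instructions might prevent double entry. That is possible, and it is why the size is given as a range that starts at zero.

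**Conclusion.** The concern holds as a gap in the counting rule. An SBP, or an infection entered as other on the complications page, can be on both pages, and SAP 9.3.10 as written would then count it twice.

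For one duplicated episode over 91 days the subject's rate doubles from 4.01 to 8.03 per year. For group rates the inflation is 0 to 30% under the assumed 10–30% overlap share and any degree of duplication. With equal duplication in both arms the ratio is unchanged and the loss of precision is small. With unequal duplication the ratio is biased in an unknown direction, by an amount that cannot be estimated from the documents.

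Only the exploratory rate analysis is touched. The primary and secondary endpoints and the percentage in SAP 9.3.9 are not.

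**What to change.** **In SAP 9.3.10**, state that the analysis counts episodes. AE-page and complications-page entries for the same subject and the same infection type or site count as one infection, dated at the earliest onset, if their dates overlap or their onsets fall within a prespecified gap. SAP 6.1.4 refers to a single complication date; if that page holds only one date, overlap should mean that this date lies within the AE's start and end dates. Apply the merge before computing the per-subject rates and fitting the Poisson model. Because the trial is open-label, fix the gap and resolve free-text matches without sight of treatment arm.

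**Reconcile the SBP instructions.** Protocol 7.2.1.1, 7.2.1.2.3 and Appendix 1 footnote g need to be squared with 8.3.3.1 and 8.3.10. SAP section 2 puts the last patient visit at April 14, 2025, so this can no longer change what sites recorded. A statement in the SAP or study report of how SBP was to be recorded, with the number of episodes found on both pages by arm, would serve.

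**Cost.** A short paragraph in the SAP, one de-duplication step in the analysis dataset, and review of a listing of candidate matches. No new data are needed.
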